**Table 3: Escape Arm Dosing Schedule by Treatment Group**

Induction Group Assignment	Maintenance Treatment Assignment	Maintenance Loading Dose (Blinded)	Week 20 to 50 (Unblinded: 250mg Q2W)
Patients entering Escape Arm at Week 16			
Active	Escape arm	Week 16: one active and one placebo injection Week 18: one active and one placebo injection	One active injection
Placebo	Escape arm	Week 16: two active injections Week 18: two active injections	One active injection
Patients entering Escape Arm at Week 24, 32, 40 and 48			
	Lebrikizumab 250 mg Q2W	At entry: one active and one placebo injection At next administration: one active and one placebo injection	One active injection
	Lebrikizumab 250 mg Q4W	At entry: one active and one placebo injection At next administration: one active and one placebo injection	One active injection
	Placebo	At entry: two active injections At next administration: two active injections	One active injection

## 5.4. Study Blinding

The Sponsor or designee, the Investigator, study-site personnel, and the patient will be blinded to treatment assignment. The integrity of the clinical study will be maintained by observing the treatment blind. If knowledge of a patient's treatment assignment is required for the patient's clinical care and/or safety, the Investigator should consult with the Sponsor's medical monitor prior to breaking the blind.

### 5.4.1. Unblinding Treatment Assignment

Unblinding the treatment assignment of a patient may only be performed in emergencies where knowledge of the patient's treatment assignment is essential for management of the patient's medical care. Unblinding the treatment assignment by the investigator under any other circumstances will be considered a protocol violation. The investigator should make every effort to contact the Sponsor or designee prior to unblinding a patient's treatment assignment. In the event of any unblinding, emergency or accidental, the sponsor must be notified within 1 business day.

Unblinding will occur using the EDC system. The Investigator must record the date and time the blind was broken, the names of the personnel involved, and the reason that treatment assignment information was required. The date and time that the Sponsor or designee was notified will also be recorded.

## **5.5. Study Drug Administration**

Study drug will be administered to all patients in the clinic by designated and trained site staff from Baseline to Week 14 (last injection prior to Maintenance Period).

### **5.5.1. Instructions for Administration in the Clinic**

Syringes should be at room temperature prior to injection (refer to the applicable Instructions for Use provided by the sponsor).

### **5.5.2. Instructions for Administration at Home**

During the Maintenance Period, patients or caregivers will be instructed to self-administer study drug during the Maintenance Period.

Study site staff will instruct the patient or their caregiver on the proper injection technique and the patient or their caregiver will demonstrate for site staff proper injection technique prior to beginning at-home administration. An instruction card with details of the injection procedures will be provided to the patient/caregiver to take home, and dosing compliance will be captured via an electronic diary.

Patients or caregivers who are not capable of administering study drug at home may continue to receive study drug injections in the clinic.

## **5.6. Study Drug Accountability**

The Investigator must keep an accurate record of the number of cartons received, the study drug dispensed/used, and those returned to the Sponsor or designee. The Sponsor or designee will provide forms to facilitate inventory control. All study-drug accountability forms and treatment logs must be retained in the Investigator's permanent study file, and these records must be available for inspection at any time by the Sponsor, its designees, or by regulatory agencies.

The study monitor will perform drug accountability for all study drug at the site, and will assist in returning all used, unused, and expired study drug, to the Sponsor/designees, or destroy it according to the study site's standard operating procedure, if accepted by the Sponsor.

## **6. CONCOMITANT MEDICATIONS AND PROCEDURES**

All medications (including over-the-counter drugs, vitamins, and antacids) and over-the-counter emollient(s) taken/used at screening and throughout the study must be recorded. Patients should be instructed to consult with the Investigator prior to initiating any new medication (either self-administered non-prescription drugs or prescription therapy prescribed by another physician) while participating in the study. The Investigator is expected to examine the acceptability of all

concomitant medications, topical preparations, and dietary supplements taken by patients participating in the trial.

- Medication entries should be specific to product name (if a combination drug product) and spelled correctly.
- The brand and specific product name for any over-the-counter emollient(s) should be noted and spelled correctly.
- Information on the dose, unit, frequency, route of administration, start date, discontinuation date, indication, and reason for use will be recorded.
- The use of any concomitant medication must relate to an AE listed on the AE eCRF or the patient's medical history unless it is a supplement or used as preventative care.

### **6.1. Permitted and Prohibited Treatments and Procedures**

The use of concomitant medications for other medical conditions (e.g., hypertension, diabetes, acute infections) is permitted during this study. Inhaled corticosteroids and bronchodilators to control asthma are permitted.

The introduction of medications or therapies for other medical conditions known to affect AD (e.g., systemic corticosteroids, mycophenolate-mofetil, IFN- $\gamma$ , Janus kinase inhibitors, TCI, cyclosporine, azathioprine, methotrexate, phototherapy, or photochemotherapy, phosphodiesterase-4 inhibitors such as crisaborole) are not permitted during the study. The use of systemic corticosteroids for the treatment of AD is prohibited and requires permanent discontinuation of Investigational Product. If used for treatment of AE (e.g. worsening of existing condition such as asthma exacerbation), it will still be treated as rescue medication as per Section 6.3.

Acute infections can be treated with systemic antibiotics, use of which must be recorded in the eCRF. However, chronic treatment with systemic antibiotics is not permitted.

The use of a tanning booth/parlor is not permitted during the trial.

Cannabinoid treatments for AD are prohibited.

Planned or anticipated major medical procedures or surgeries should be avoided during the trial.

See Section 6.3 for details on approved rescue medications and timing of use.

### **6.2. Moisturizers**

Non-medicated moisturizers are to be used during the study. The patient may continue her/his current over-the-counter moisturizer regimen, if approved by the Investigator.

### **6.3. Rescue Treatment for Atopic Dermatitis**

#### **Induction Period**

The use of topical or systemic treatments for atopic dermatitis is prohibited from Baseline through Week 16 in this study. Patients who experience intolerable AD symptoms and require treatment should, preferably, be started on topical treatments (e.g., mid-potency TCS) prior to instituting systemic treatments for AD symptoms, in accordance with best practice.

If systemic rescue treatments (e.g., oral corticosteroids, phototherapy, cyclosporin, etc.) are required, study drug must be discontinued. The patient should continue to attend all study visits through Week 16 and be assessed for safety and efficacy according to the schedule of events.

Patients requiring topical or systemic rescue medication who complete the study through Week 16 will be eligible to continue to the Escape Arm after the Week 16 visit has been completed. Patients who required systemic rescue medication must wait for rescue medication washout ( $\geq 5$  half-lives of the medication) prior to entering the Escape Arm.

### **Maintenance Period**

Intermittent use of topical rescue medications for AD is permitted during the Maintenance Period. Patients who may require short-term systemic treatment for symptoms of AD during the Maintenance Period will be assessed on a case by case basis and must be discussed with the Medical Monitor prior to initiating treatment.

### **Escape Arm**

Intermittent use of topical rescue medications for AD is permitted for patients who are in the Escape Arm. Patients who may require short-term systemic treatment for symptoms of AD during the Escape Arm will be assessed on a case by case basis and must be discussed with the Medical Monitor prior to initiating treatment. Patients requiring long-term systemic treatment for symptoms of AD in the Escape Arm (e.g., non-responders) must be discontinued from the study.

The Sponsor may supply the study sites with a mid-potency and a low-potency TCS that can be provided to patients for use, if needed (e.g., triamcinolone acetonide 0.1% cream and hydrocortisone 1% cream).

All topical and systemic treatments for AD must be captured in the eCRF.

## **7. STUDY PROCEDURES**

The required procedures for each study visit are outlined in [Appendix 1](#). The timing of each study day is relative to the day of initial dosing (Day 1, Baseline).

### **7.1. Screening Visit**

The purpose of the screening visit/period is to ensure that appropriate patients are entered into the study and that they remain stable during the pre-treatment period.

- Obtain written informed consent/assent prior to performing any study procedures
- Review Inclusion/Exclusion Criteria
- Complete medical history/review of systems
- Review immunization record for adolescent patients
- Collect demographic information
- Measure vital signs
- Perform a complete physical examination, including height and weight

- Collect concomitant medication and procedure/therapy information
- Complete the following assessments: Investigator's Global Assessment (IGA), Body Surface Area (BSA), and Eczema Area and Severity Index (EASI)
- Draw blood samples for laboratory tests, including serum pregnancy
- Collect urine sample for urinalysis
- Assign eDiary and instruct the patient on the completion of the following assessments: Pruritus and Sleep-Loss (daily), and POEM (weekly)
- Instruct the patient to apply a moisturizer at least twice daily

## 7.2. Baseline Visit (Day 1) Induction Period

- Administer the DLQI/CDLQI and EQ-5D
- Administer the PROMIS (Patient-Reported Outcomes Measurement Information System): Anxiety and Depression measures
- Collect the ACQ-5 assessment for patients with comorbid asthma
- Update medical history/review of systems and concomitant medication and procedure/therapy information
- Complete the following assessments: IGA, BSA, EASI and SCORAD
- Review compliance report on the eDiary and confirm moisturizer use
- Measure vital signs
- Draw a pre-dose blood sample for PK and anti-drug antibody (ADA) testing
- Conduct urine pregnancy test (WOCBP only)
- Re-assess and confirm patient eligibility (Inclusion/Exclusion criteria)
- Randomize the patient, receive kit assignment, and administer study drug
- Remind patient to record the following: Pruritus and Sleep-Loss (daily), and POEM (weekly)

Sites collecting photos will also:

- Obtain written informed consent for collecting photos
- Select a target lesion and obtain a photograph

## 7.3. Week 2 ( $\pm$ 3 Days)

- Complete the following assessments: IGA, BSA and EASI
- Review and record AEs and update concomitant medication and procedure/therapy information
- Review compliance report on the eDiary, confirm moisturizer use and remind patient to record the following: Pruritus and Sleep-Loss (daily), and POEM (weekly)

- Measure vital signs
- Administer study drug

Sites collecting photos will also:

- Obtain photographs of the target lesion

#### **7.4. Week 4 ( $\pm$ 3 Days)**

- Administer the DLQI/CDLQI
- Complete the following assessments: IGA, BSA and EASI
- Review and record AEs and update concomitant medication and procedure/therapy information
- Measure vital signs
- Draw a pre-dose blood sample for PK and ADA testing
- Conduct urine pregnancy test (WOCBP only)
- Administer study drug
- Review compliance report on the eDiary, confirm moisturizer use and remind patient to record the following: Pruritus and Sleep-Loss (daily), and POEM (weekly)

#### **7.5. Week 6 ( $\pm$ 3 Days)**

- Complete the following assessments: IGA, BSA, and EASI
- Review and record AEs and update concomitant medication and procedure/therapy information
- Review compliance report on the eDiary, confirm moisturizer use and remind patient to record the following: Pruritus and Sleep-Loss (daily), and POEM (weekly)
- Measure vital signs
- Administer study drug

#### **7.6. Week 8 ( $\pm$ 3 Days)**

- Administer the DLQI/CDLQI
- Complete the following assessments: IGA, BSA and EASI
- Review and record AEs and update concomitant medication and procedure/therapy information
- Review compliance report on the eDiary, confirm moisturizer use and remind patient to record the following: Pruritus and Sleep-Loss (daily), and POEM (weekly)
- Measure vital signs
- Draw blood samples for laboratory tests, except hormones

- Collect a urine sample for urinalysis
- Conduct urine pregnancy test (WOCBP only)
- Administer study drug

Sites collecting photos will also:

- Obtain photographs of the target lesion

### **7.7. Week 10 ( $\pm$ 3 Days)**

- Complete the following assessments: IGA, BSA, EASI
- Review and record AEs and update concomitant medication and procedure/therapy information
- Review compliance report on the eDiary, confirm moisturizer use and remind patient to record the following: Pruritus and Sleep-Loss (daily), and POEM (weekly)
- Measure vital signs
- Administer study drug

### **7.8. Week 12 ( $\pm$ 3 Days)**

- Administer the DLQI/CDLQI
- Complete the following assessments: IGA, BSA and EASI
- Review and record AEs and update concomitant medication and procedure/therapy information
- Review compliance report on the eDiary, confirm moisturizer use and remind patient to record the following: Pruritus and Sleep-Loss (daily), and POEM (weekly)
- Measure vital signs
- Conduct urine pregnancy test (WOCBP only)
- Administer study drug

### **7.9. Week 14 ( $\pm$ 3 Days)**

- Complete the following assessments: IGA, BSA and EASI
- Review and record AEs and update concomitant medication and procedure/therapy information
- Review compliance report on the eDiary, confirm moisturizer use and remind patient to record the following: Pruritus and Sleep-Loss (daily), and POEM (weekly)
- Measure vital signs
- Administer study drug

**7.10. Week 16 ( $\pm$  3 Days) Transition to Maintenance Period**

- Administer the DLQI/CDLQI, and EQ-5D
- Administer the PROMIS measures
- Collect ACQ-5 for patients with comorbid asthma
- Complete the following assessments: IGA, BSA, EASI and SCORAD
- Perform a complete physical examination, including height and weight
- Review and record AEs and update concomitant medication and procedure/therapy information
- Review compliance report on the eDiary, confirm moisturizer use and remind patient to record the following: Pruritus and Sleep-Loss (daily), and POEM (weekly)
- Measure vital signs
- Draw pre-dose blood samples for laboratory tests, PK and ADA testing
- Collect a urine sample for urinalysis
- Conduct urine pregnancy test (WOCBP only)
- Re-randomize the patient to the Maintenance Period
- Train the patient to self-administer study drug
- Administer one injection and observe the patient self-injecting
- Dispense study drug for Week 18 injections

Sites collecting photos will also:

- Obtain a photograph of the target lesion

**7.11. Week 20 ( $\pm$  5 Days)**

- Complete the following assessments: IGA, BSA and EASI
- Review and record AEs and update concomitant medication and procedure/therapy information
- Review compliance report on the eDiary, confirm moisturizer use and remind patient to record the following: Pruritus and Sleep-Loss (daily), and POEM (weekly)
- Measure vital signs
- Conduct urine pregnancy test (WOCBP only)
- Administer or observe the patient self-injecting study drug
- Dispense study drug for Week 22 injection
- Remind the patient to apply moisturizer and to complete the eDiary as instructed

**7.12. Week 24 ( $\pm$  5 Days)**

- Complete the following assessments: IGA, BSA and EASI
- Review and record AEs and update concomitant medication and procedure/therapy information
- Review compliance report on the eDiary, confirm moisturizer use and remind patient to record the following: Pruritus and Sleep-Loss (daily), and POEM (weekly)
- Measure vital signs
- Conduct urine pregnancy test (WOCBP only)
- Administer or observe the patient self-injecting study drug
- Dispense study drug for Week 26 injection
- Remind the patient to apply moisturizer and to complete the eDiary as instructed

**7.13. Week 28 ( $\pm$  5 Days)**

- Complete the following assessments: IGA, BSA and EASI
- Review and record AEs and update concomitant medication and procedure/therapy information
- Review compliance report on the eDiary, confirm moisturizer use and remind patient to record the following: Pruritus and Sleep-Loss (daily), and POEM (weekly)
- Measure vital signs
- Conduct urine pregnancy test (WOCBP only)
- Administer or observe the patient self-injecting study drug
- Dispense study drug for Week 30 injection
- Remind the patient to apply moisturizer and to complete the eDiary as instructed

**7.14. Week 32 ( $\pm$  5 Days)**

- Administer the DLQI/CDLQI
- Complete the following assessments: IGA, BSA and EASI
- Perform a complete physical examination, including height and weight
- Review and record AEs and update concomitant medication and procedure/therapy information
- Review compliance report on the eDiary, confirm moisturizer use and remind patient to record the following: Pruritus and Sleep-Loss (daily), and POEM (weekly)
- Measure vital signs
- Draw blood samples for laboratory tests, PK and ADA testing

- Collect a urine sample for urinalysis
- Conduct urine pregnancy test (WOCBP only)
- Administer or observe the patient self-injecting study drug
- Dispense study drug for Week 34 injection
- Remind the patient to apply moisturizer and to complete the eDiary as instructed

### **7.15. Week 36 ( $\pm$ 5 Days)**

- Complete the following assessments: IGA, EASI, and BSA
- Review and record AEs and update concomitant medication and procedure/therapy information
- Review compliance report on the eDiary, confirm moisturizer use and remind patient to record the following: Pruritus and Sleep-Loss (daily), and POEM (weekly)
- Measure vital signs
- Conduct urine pregnancy test (WOCBP only)
- Administer or observe the patient self-injecting study drug
- Dispense study drug for Week 38 injection
- Remind the patient to apply moisturizer and to complete the eDiary as instructed

### **7.16. Week 40 ( $\pm$ 5 Days)**

- Complete the following assessments: IGA, BSA and EASI
- Review and record AEs and update concomitant medication and procedure/therapy information
- Review compliance report on the eDiary, confirm moisturizer use and remind patient to record the following: Pruritus and Sleep-Loss (daily), and POEM (weekly)
- Measure vital signs
- Conduct urine pregnancy test (WOCBP only)
- Administer or observe the patient self-injecting study drug
- Dispense study drug for Week 42 injection
- Remind the patient to apply moisturizer and to complete the eDiary as instructed

### **7.17. Week 44 ( $\pm$ 5 Days)**

- Complete the following assessments: IGA, EASI, and BSA
- Review and record AEs and update concomitant medication and procedure/therapy information

- Review compliance report on the eDiary, confirm moisturizer use and remind patient to record the following: Pruritus and Sleep-Loss (daily), and POEM (weekly)
- Measure vital signs
- Conduct urine pregnancy test (WOCBP only)
- Administer or observe the patient self-injecting study drug
- Dispense study drug for Week 46 injection
- Remind the patient to apply moisturizer and to complete the eDiary as instructed

### **7.18. Week 48 ( $\pm$ 5 Days)**

- Complete the following assessments: IGA, BSA and EASI
- Review and record AEs and update concomitant medication and procedure/therapy information
- Review compliance report on the eDiary, confirm moisturizer use and remind patient to record the following: Pruritus and Sleep-Loss (daily), and POEM (weekly)
- Measure vital signs
- Conduct urine pregnancy test (WOCBP only)
- Administer or observe the patient self-injecting study drug
- Dispense study drug for Week 50 injection
- Remind the patient to apply moisturizer and to complete the eDiary as instructed

### **7.19. Week 52 ( $\pm$ 5 Days) End of Study**

- Administer the DLQI/CDLQI, and EQ-5D
- Administer the PROMIS measures
- If the patient has reported a history of asthma, collect the ACQ-5 assessment
- Complete the following assessments: IGA, BSA, EASI and SCORAD
- Perform a complete physical examination, including height and weight
- Review and record AEs and update concomitant medication and procedure/therapy information
- Review compliance report on the eDiary and collect eDiary
- Measure vital signs
- Draw blood samples for laboratory tests, PK and ADA testing
- Collect a urine sample for urinalysis
- Conduct urine pregnancy test (WOCBP only)

## 7.20. Early-Termination Visit

Patients who discontinue the study early for any reason should have these assessments performed at their early-termination visit. The reason for early termination must be recorded in the eCRF (see Section 8.7.1).

- Administer the DLQI/CDLQI, and EQ5D
- Administer the PROMIS measures
- Collect the ACQ-5 assessment for patients with comorbid asthma
- Complete the following assessments: IGA, BSA, EASI and SCORAD
- Perform a complete physical examination, including height and weight.
- Review and record AEs and update concomitant medication and procedure/therapy information
- Review compliance report on the eDiary and collect eDiary
- Measure vital signs
- Draw blood samples for laboratory tests, PK and ADA testing
- Collect a urine sample for urinalysis
- Conduct urine pregnancy test (WOCBP only)

If the Early Termination Visit is during the Induction Period, sites collecting photos will also:

- Obtain a photograph of the target lesion

## 7.21. Safety Follow-up Visit

Patients who terminate early from the study or do not enroll in the long-term extension study, DRM06-AD07, will undergo a follow up visit approximately 12 weeks after the last study drug injection.

- Update AEs and concomitant medications and procedures that were ongoing at study termination.
- Draw blood samples for PK and ADA testing.

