### 3.1. Duration of the Study

The total duration of a patient's participation in this study will be approximately 66 weeks (Screening: maximum duration of 30 days; Induction Period: 16 weeks; Maintenance Period: 36 weeks; Follow Up: 12 weeks from last dose at Week 50).

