#### 8.5.4. Adverse Events

Adverse events will be monitored throughout the study. Patients will be instructed to inform the Investigator and/or study staff of any AEs. At each visit, patients will be asked about AEs in a non-specific manner using open-ended questions so as not to bias the response (e.g., How have you been since the last visit?). Specific inquiry regarding reported AEs will be conducted when applicable. All AEs will be documented and recorded in the patient's eCRF.

Any patient who has an AE (serious or non-serious) will be evaluated by the Investigator and treated and followed until the symptom(s) return to normal or to clinically acceptable levels, as judged by the Investigator. A physician, either at the clinical site, or at a nearby hospital

emergency room, will administer treatment for any serious AEs (SAEs), if necessary. When appropriate, medical tests and examinations will be performed to document resolution of event(s).

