#### 8.5.4.1. Reporting

Only AEs that occur during or following study treatment with the study drug will be reported in the AE section of the eCRF. Events occurring prior to study treatment with the drug will be reported in the Medical History section of the eCRF. All AEs occurring during the study will be individually recorded in the eCRF. Any condition present prior to administration of study drug and that worsens after administration of study drug should be reported as an AE. Information regarding the onset, duration, severity, action taken, outcome, and relationship to study drug will be recorded.

New or worsening abnormal laboratory values and/or vital signs are to be recorded as AEs if they are considered to be of clinical significance by the Investigator or meet the criteria of an SAE as described in Section 8.5.4.3. Unless an overall diagnosis is described, signs and symptoms must be reported as individual AEs in the eCRF; a diagnosis is preferred.

The severity of an AE will be designated as mild, moderate or severe. The term “severe” is used to describe the intensity of an AE; the event itself, however, may be of relatively minor clinical significance (e.g., ‘severe’ upper respiratory infection). Severity is not the same as “serious”. Seriousness of AEs is based on the outcome/action of an AE. (See Section 8.5.4.3.)

The relationship of the AE to the study treatment should be determined by the Investigator and will be based on the following two definitions:

**Not related:** The AE is judged to not be associated with the study drug and is most likely attributable to another cause.

**Related:** A causal relationship between the AE and the study drug is a reasonable possibility, i.e., there is evidence (e.g., dechallenge/rechallenge) or other clinical arguments to suggest a causal relationship between the AE and study treatment.

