6.1.4. General Considerations for Safety Analyses for Combined Induction and Maintenance Periods

Adverse event, exposure summary, and categorical laboratory/vital sign changes will be provided for the All Lebrikizumab Safety Population during the Combined Induction and Maintenance Periods. For patients who were first exposed to lebrikizumab during Induction Period, the baseline for TEAE will utilize the baseline for Induction Period defined in Section 6.1.2; for patients who were first exposed to lebrikizumab during Maintenance Period, the baseline for TEAE will utilize the baseline for Maintenance Period defined in Section 6.1.3.

More details on baseline and postbaseline definitions can be found in the Compound Level Safety Standard.

6.1.5. General Considerations for Safety Analyses for Combined Induction and Maintenance Periods Plus Follow Up Period

Selective AE summaries will be provided for the All Lebrikizumab Safety Population during the Combined Induction and Maintenance Periods plus Follow up Period. The baseline definition

for this population is the same as Section 6.1.4. More details on baseline and postbaseline definitions can be found in the Compound Level Safety Standard.

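### Protocol 7.21 words the Safety Follow-up visit as an update of ongoing adverse events, which contradicts the rules elsewhere that new events be asked about and recorded at every visit

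*Protocol*

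**What the plan says.** Protocol 7.21 applies to patients who terminate early or do not enrol in DRM06-AD07. They "will undergo a follow up visit approximately 12 weeks after the last study drug injection". Sites have two tasks at that visit: "Update AEs and concomitant medications and procedures that were ongoing at study termination", and draw PK and ADA samples.

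Other parts of the plan bear on the same visit:

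- Week 52 (Protocol 7.19) says: "Review and record AEs and update concomitant medication and procedure/therapy information". Weeks 2 to 48, the Early-Termination visit (7.20) and unscheduled visits (7.22) use the same instruction.
- Protocol 8.5.4 says: "Adverse events will be monitored throughout the study". It adds: "At each visit, patients will be asked about AEs in a non-specific manner using open-ended questions".
- Protocol 8.5.4.1 makes events during or after treatment reportable and says: "All AEs occurring during the study will be individually recorded in the eCRF".
- Protocol Section 7 refers sites to Appendix 1 for the required procedures. Table 7 there marks adverse events in the Safety F/U column, with no limit to ongoing events.
- The Synopsis and Section 3 make this visit part of completing the study for patients who do not continue into the extension.
- SAP 6.1.5 says: "Selective AE summaries will be provided for the All Lebrikizumab Safety Population during the Combined Induction and Maintenance Periods plus Follow up Period". SAP 6.14.1 adds any follow-up period to exposure for the same population and window.

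**The concern.** Section 7.21 is the visit-specific instruction, and sites commonly work through such lists item by item. It is the only post-baseline visit list that drops the verb for recording AEs and adds a condition that they were ongoing at termination. A site that follows it closes out known events and has no prompt to ask what has happened since.

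The patients concerned are those who stopped early, including for an adverse event or after failing to reach EASI-50 in the Escape Arm, and those who declined the extension. The protocol plainly means to observe them after treatment, since it brings them on site and draws PK and ADA samples. What is at stake is whether new non-serious events in that interval are collected, and whether they are collected in the same way at about 100 sites.

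**Working it through.** No power, alpha or event count is at issue. The check compares the texts and does calendar arithmetic.

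**1. Instructions side by side**

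| Place | What the site is to do about AEs | New events covered? |
|---|---|---|
| Protocol 7.3 to 7.20, 7.22 | Review and record | Yes |
| Protocol 7.21 | Update those ongoing at termination | Not on the natural reading |
| Protocol 8.5.4 | Ask openly at each visit | Yes |
| Protocol 8.5.4.1 | Record all during the study | Yes |
| Appendix 1, Table 7, Safety F/U | Marked, no restriction | Yes |

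**2. Grammar of 7.21.** The condition about being ongoing can attach to AEs, medications and procedures together, or to medications and procedures alone. The first reading excludes new AEs. The second leaves a bare instruction to update AEs, which still does not say to record new ones.

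**3. Interval that depends on 7.21.** Protocol 3.1 gives "Follow Up: 12 weeks from last dose at Week 50".

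- Follow-up visit: Week 50 + 12 = Week 62.
- Week 52 (±5 days) already records new AEs, so the interval for a Week 52 completer is 62 − 52 = about 10 weeks.
- Check against the plan's own total: 30 days ÷ 7 = 4.3 weeks, and 4.3 + 50 + 12 = 66.3 weeks, which matches the stated 66.
- For early terminators the interval starts at the ET visit, scheduled as soon as possible. The documents do not fix its length.

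**4. Which events rely on being asked about.** SAEs have their own window in 8.5.4.4, from consent to the end of the study. AESIs have their own rule in 8.5.4.2: they are reported within 48 hours of knowledge. That rule acts only once the site knows, and for a non-serious conjunctivitis or herpes episode knowledge may depend on a question. Other non-serious AEs rest on 8.5.4 and 8.5.4.1, which carry no explicit end date of the kind given for SAEs.

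**5. Path into the analysis.** Under SAP 6.14.2 a TEAE must first occur or worsen after baseline. Updating an event that is already open adds a TEAE to the follow-up window only if that event worsens, so additional TEAEs there come mainly from new onsets. Under SAP 6.14.1 the follow-up time counts as exposure whether or not new events were sought.

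**6. What cannot be computed.** The number of missed events would need the proportion of patients who have this visit, the new-onset AE rate during follow-up, and the share of sites that follow 7.21 rather than 8.5.4. The documents give none of the three.

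**The case against.** The strongest reply is that the rest of the protocol already requires new events to be collected. Section 7 sends sites to Appendix 1, Table 7 marks AEs at this visit, 8.5.4 covers each visit, and 8.5.4.1 covers all AEs in the study. Section 7.21 does not say that only ongoing events count, and it can be read as adding close-out to the general duty. Patients are told to report any AE, and unscheduled visits record AEs.

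Most of this stands, and it rules out several stronger readings that a reader might infer:

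- **That new events at this visit go uncaptured.** The documents do not support this. It would require sites to disregard 8.5.4, 8.5.4.1 and Table 7.
- **That non-serious AESIs have no reporting rule.** They do, in 8.5.4.2. The weak point is only how the site comes to know of the event.
- **That the full 12 weeks are exposed.** The Week 52 or ET visit covers the first part.
- **That a post-treatment AE table would look falsely clean.** No stand-alone table is planned. SAP 6.1.5 and Table KGAB.6.2 give selective summaries pooled over induction, maintenance and follow-up, in one lebrikizumab group without comparisons. Postbaseline definitions are left to a compound-level standard that is not part of these documents.

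The reply does not remove the conflict. The general sections show the intent, but a site may take the narrower, visit-specific text as the exception, and nothing says which governs.

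**Conclusion.** The point holds as an internal contradiction: 7.21 is wrong as written and should be corrected. Sites may differ in whether they ask about non-serious AEs, or learn of non-serious AESIs, that start between the Week 52 or ET visit and the follow-up visit. For Week 52 completers that interval is about 10 weeks, assuming the last dose at Week 50 and visits on schedule.

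The possible consequence is an under-count, uneven across sites, in the pooled AE summaries that include follow-up. SAP 6.14.2 describes numbers and percentages of patients. A rate per unit of exposure would also be lowered, but only if one were formed with the follow-up time in the denominator.

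A reader might want this expressed in patient-years or missed events. That would rest on a guessed rate of non-entry into the extension, so no figure is given. The conclusion also rests on the natural reading of 7.21. On the alternative reading in step 2 the text is ambiguous rather than restrictive, and it still needs correction. The follow-up eCRF page is not in the documents, so whether it accepts new events is unknown.

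**What to change.** 1. Replace the AE bullet in Protocol 7.21 with the instruction used at the other visits: "Review and record AEs and update concomitant medication and procedure/therapy information".
2. State in 7.21 or 8.5.4.1 that new as well as ongoing AEs and AESIs are recorded through the Safety Follow-up visit. This gives non-serious events an explicit end date.
3. Confirm that the follow-up eCRF page and its completion guide allow new events to be entered.

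The cost is one bullet, one sentence and an eCRF check. The visit is already on site, so the only downside is a few more recorded AEs. The SAP text needs no change.
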